
in subjects with type 2 diabetes and pre-existing cardiovascular disease (48). Collectively these results indicate that pioglitazone, in addition to lowering plasma glucose concentration, reduces insulin resistance, preserves beta cell function, and may have a direct action on the vasculature (74) to reduce the vascular complications of diabetes above and beyond its glucose lowering effect.

Exenatide is a GLP-1 mimetic drugs which binds to the GLP-1 receptor on the beta cell and markedly augments glucose-stimulated insulin secretion (75,76). Because its stimulatory effect on insulin secretion is glucose dependent, hypoglycemia is rarely encountered when exenatide is used as monotherapy or in combination with metformin or a thiazolidinedione (77-79). Exenatide also acts on the alpha cell to suppress glucagon secretion (78). The combination of increased insulin secretion and decreased glucagon secretion results in suppression of basal/post-meal hepatic glucose production (HGP) and enhanced peripheral tissue (muscle) glucose disposal (80). Clinical studies have demonstrated that exenatide causes a significant reduction in fasting (decreased HGP) and post-prandial (increased muscle glucose uptake) plasma glucose concentration, leading to a significant drop in HbA_{1c} (79-84), and is well tolerated when added to metformin (84) or to a thiazolidinedione (79). Exenatide also has extrapancreatic actions: it delays gastric emptying, thereby reducing postprandial hyperglycemia (85), and suppresses appetite, resulting in significant weight loss (86,87). The weight loss is associated with a decrease in plasma triglycerides, an increase in plasma HDL concentration, and a reduction in blood pressure (80-86). These latter actions of exenatide would be expected to have a favorable effect to reduce cardiovascular complications (88,89). Studies in humans have demonstrated that exenatide markedly enhances beta cell function in subjects with type 2 diabetes (90). In experimental animals exenatide stimulates beta cell neogenesis and replication and inhibits beta cell apoptosis (91). If these later effects were to extend to humans, additional beneficial effects on beta cell health would be expected.

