Following completion of these tests, subjects will be randomized (using a table of random numbers) to receive, in open label fashion, one of the following treatment regimens: (i) Group I will be started on pioglitazone (15 mg/day) plus metformin (1000 mg/day) with the supper meal and exenatide (5 mcg s.c. bid 30 min before breakfast and supper) and up-titrated to 45 pioglitazone plus 2000 metformin and 10 mcg s.c. bid exenatide to achieve HbA1c <6.0%; (II) Group II will be started on metformin, 1000 mg with breakfast and 1000 mg with supper, glyburide and basal insulin will be added and up titrated to achieve HbA1c <6.0% Subjects will be recruited during the first year and followed up for additional two years. After completing the repeat studies, subjects will be asked to continue in the study and with the study medications without any change. Follow up visits will occur every 3 months) until the last patient recruited into the study completes 2 –years of follow-up. At the Follow visit Fasting Glucose and HbA1C will be performed. At the annual visits blood work to check the following: fasting glucose, HbA1C, and other repeat labs. Every 2 years or if the subject decides to discontinue participation, we will repeat the annual labs, OGTT, eye photographs, and carotid ultrasound.

4. Study Population(s).

You will be drawing subjects from one or more populations. In medical research, for example, a population can be individuals with type 2 diabetes controlled with diet, or a population of healthy individuals. In social behavioral research, a population can be individuals attending an education program, etc.

- a. How many different populations are you enrolling in this study?
- b. For each different population, provide a short descriptive label: (e.g., *normal-healthy, diabetics, patients needing surgery, parents, child, etc.*)

1

720 Newly diagnosed type 2 diabetic subjects
Will be enrolled to have 600 completers .

For each **specific** population identified 4b, provide the following information in the table provided below. (**One table is provided, use copy and paste for additional tables if enrolling more than one population.**)

Population # [Type # given to population in 4b]	Population Descriptive Label: [Insert short label from 4b] Enrollment of [Insert #] requested to obtain [Insert #] completers.
XCheck here if enrolling only one population	
(1)	Identify the criteria for inclusion :

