If, after month six, the HbA_{1C} $> 6.0\%$, and the subject is on maximum doses of metformin, glipizide, and glargine insulin, the subject will be considered a treatment failure. Regular insulin will be added to each meal when the HbA_{1C} rises to $> 6.5\%$ and adjusted based upon the pre- and post-meal blood glucose levels. These "treatment failure" subjects will continue with all follow up visits/procedures.

Throughout the titration process, downward adjustments will be allowed for the development of hypoglycemia, as defined by a blood glucose less than 60 mg/dl with (symptomatic hypoglycemia) or without (asymptomatic hypoglycemia) symptoms. Serious hypoglycemia is defined as any hypoglycemic reaction requiring assistance from a third party for recovery.

Following their enrollment into the study, all T2DM participants will return to the Clinical Research Center (CRC) at the TDI for follow up visits every 3 months. Telephone calls also will be made to each participant every 6 weeks. During the telephone/CRC visits, subjects will be asked questions about interim medical history, home glucose monitoring results, and compliance with the medical regimen.

During each 3-month follow-up visit to the CRC, body weight, waist circumference (Gulick III tape measure), and blood pressure (Dynamap) will be measured. Blood will be drawn for FPG and HbA_{1c}, and pharmacological therapy will be adjusted based on the HbA_{1c}, FPG, and HBGM results (see prior algorithm). Plasma lipids and 24-hour urine albumin excretion will be measured annually or more frequently as indicated by test results. In addition to glycemic control, all subjects will receive therapy for any abnormal cardiovascular risk factors: hypercholesterolemia (goal LDL <100 mg/dl), hypertriglyceridemia (goal <150 mg/dl), hypertension (goal <130/80 monthly), albumin excretion (goal < 30 mg/day). At the end of three years, the OGTT, DEXA, fundus photography, 24 hour urine for albumin, hyperglycemic clamp, ankle-arm blood pressure, and carotid IMT will be repeated.

Primary End Point: The primary end point of the study is the difference in HbA_{1c} between Group I (triple combination therapy at time of initial diagnosis) and Group II (stepwise therapy).

Secondary End Points: The following parameters will be measured as secondary endpoints;

- 1) Number of subjects in each group with HbA_{1c} < 6.0%

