- 2) Number of treatment failures in each group as defined by HbA_{1c} >6.0% and requiring the addition of rapid acting insulin with meals
- 3) Change in beta cell function
- 4) Change in whole body insulin resistance
- 5) Incidence of hypoglycemia (asymptomatic, symptomatic, serious)
- 6) Change in body weight, total body fat, and waist circumference
- 7) Change in carotid intima media thickness
- 8) Change in ankle-arm blood pressure
- 9) Change in stage of diabetic retinopathy

Change in GFR and urinary albumin secretion rate

Subjects who will complete 3-year follow-up and the repeat studies will continue to receive therapy as described above and continue in the follow-up visit every 3 months as previously described until the last subjects recruited to the study has completed 2-year follow-up. During this follow up period we will repeat the OGTT, eye photographs, DEXA and carotid ultrasound every other year (Year 3 and 6).

Washout Phase

At 6 years, all baseline studies will be repeated as stated above (OGTT, annual labs, eye photographs, ankle-arm blood pressure and carotid ultrasound). After the completion of the repeat studies, hepatic fat content and liver fibrosis will be measured with fibroscan and MRI Spectroscopy.

MRI Spectroscopy is the gold standard method to quantitate hepatic fat content. Pharmacologic therapy will be stopped if participants HbA1C is less than 7.5%. Participants with HbA1C greater than 7.5% and in the triple therapy arm, dapagliflozin (10mg/day) will be added. Participants with HbA1C greater than 7.5% in the conventional therapy arm will be switched to triple therapy. Patients will be seen every 3 months for a follow-up visit. Medical history, physical exam, body weight, blood pressure, Fasting blood sugar and HbA1c will be measured at each follow-up visit. The OGTT will be repeated at 3 months and every 6 months thereafter. Liver fat content and liver fibrosis will be measured with fibroscan annually. The 3-month follow-up visits will continue for additional 5 years, to obtain information about the long-term durability of triple therapy. Liver fat content and liver fibrosis will be measured with fibroscan and MRI annually, and the OGTT will be repeated every 2 years, and all baseline measurements will be repeated at 5 years.

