Type 2 diabetes mellitus (T2DM) is a common metabolic disease that affects 21 million Americans and is associated with significant morbidity and mortality secondary to micro- and macrovascular complications. Subjects with T2DM manifest insulin resistance in skeletal muscle, liver and adipocytes and impaired insulin secretion. Although many therapeutic agents have been developed to target the pathogenic abnormalities in subjects with T2DM, the current ADA recommendation for pharmacological therapy in T2DM remains based on monotherapy, with dose escalation, followed by sequential addition of oral antidiabetic agents and eventually insulin to control blood glucose levels. Unfortunately, the majority of type 2 diabetic individuals in the US fail to achieve the recommended level of glycemic control ($\text{HbA}_{1c} < 6.0\%$) using this approach. In this study, I propose to explore the efficacy of a novel therapeutic approach to attain glycemic control in T2DM subjects. This novel approach is based upon the initiation of triple combination therapy at the time of diagnosis with agents that target specific pathogenic abnormalities present in T2DM. Two groups of newly diagnosed, drug naive T2DM subjects will be studied: (i) Group I will receive triple combination therapy with metformin, pioglitazone, and exenatide as initial therapy; (ii) Group II will be started on metformin monotherapy followed by sequential addition of a sulfonylurea and then glargin insulin. The goal of therapy in both groups is to reduce the $\text{HbA}_{1c} < 6.0\%$. Subjects will be recruited over one year and followed for 2 years (total study duration =3 years). The primary outcome will be the difference in HbA_{1c} between Groups I and II. Secondary outcomes will include failure to achieve the glycemic goal ($\text{HbA}_{1c} < 6.0\%$), improvements in insulin resistance, beta cell function, markers of inflammation, markers of oxidative stress, and carotid intima media thickness. I hypothesize that subjects started on combination therapy at the time of diagnosis of T2DM will have better and more durable glycemic control, a lower rate of therapeutic failure, enhanced insulin sensitivity, and improved/preservation of beta cell function compared to subjects receiving the “conventional” ADA-recommended stepped-therapeutic approach with “standard” medications. I also hypothesize that subjects started on initial combination therapy will have: (i) lower levels of inflammatory markers and (ii) reduced carotid IMT. On a long-term basis, one would expect the superior metabolic control in T2DM who receive aggressive combination therapy from onset to have a lower rate of diabetic complications.

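### Beta-cell function is tested during continuing therapy, so a between-arm difference in secondary endpoint 3 cannot by itself support preservation, and no analysis is planned for the off-drug OGTT

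*Combined protocol and SAP*

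**What the plan says.** Section 6a lists secondary endpoint 3 as "Change in beta cell function", with no index, time point or drug state. The Abstract predicts "improved/preservation of beta cell function compared to subjects receiving" the stepped approach. Section 1 states the beta-cell objective as improvement only.

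Section 4 admits people on diet or metformin only. Beta-cell function is then measured by OGTT indices and, in 25 subjects per group, by hyperglycemic clamp (section 3). The repeat tests come at year 3 ("At the end of three years, the OGTT, DEXA, fundus photography", with the clamp later in the same list). Treatment continues around them: section 3 says "subjects will be asked to continue in the study and with the study medications without any change", and section 6a says "Subjects who will complete 3-year follow-up and the repeat studies will continue to receive therapy as described above". The OGTT and clamp methods mention no withholding of study drug. Section 6a also places the year-6 repeat tests before any drug is stopped.

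Section 2 says that exenatide "markedly augments glucose-stimulated insulin secretion" and that it slows gastric emptying. In section 6a, Group II may receive glipizide, basal insulin and mealtime insulin.

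In the Washout Phase, therapy stops if year-6 HbA1c is below 7.5%. Above that value, the triple-therapy arm adds dapagliflozin and the conventional arm switches to triple therapy. The text then says "The OGTT will be repeated at 3 months and every 6 months thereafter". The Data Analysis section mentions neither beta-cell function nor the washout.

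**The concern.** The change score compares a baseline free of exenatide, sulfonylurea and insulin with a test taken under continuing treatment that differs by arm. Exenatide can raise the numerator of the secretion index by stimulating secretion, and lower the glucose denominator by slowing gastric emptying, with no lasting change in the beta cell. Glipizide also stimulates secretion. Injected insulin enters the plasma-insulin indices directly. The year-3 and year-6 contrasts therefore mix any durable difference with differences in current drug action.

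The Background argues that durable control depends on halting beta-cell failure, so readers will look to endpoint 3 for the mechanism. The OGTT after stopping could help to separate the two explanations, but it is tied to no endpoint or analysis. It is also off drug only for participants whose HbA1c, itself affected by treatment, was below the threshold.

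**Working it through.** **The plan's own figure.** The plan gives no sample size for endpoint 3. For HbA1c it gives 76 completers per arm, for a difference of 0.5 and an SD read as 0.95 (the printed value is garbled). With two-sided alpha 0.05 and 90% power (power is not stated):

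n = 2 × (1.960 + 1.282)² × 0.95² / 0.5² = 75.9, so 76. It reproduces.

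**Could drug action alone produce a significant difference?**

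Inputs:
- 300 per arm: the 600 completers in section 4, assuming equal allocation.
- 76 per arm: the sample-size section.
- 25 per arm: the clamp subgroup.
- Between-subject coefficient of variation 50%, and acute effects of 10% and 20%: assumptions, since the documents give neither.

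With zero durable effect, SE = 0.5 × √(2/n) and z = acute effect / SE.

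| n per arm | SE | z, 10% effect | z, 20% effect |
|---|---|---|---|
| 300 | 0.041 | 2.4 | 4.9 |
| 76 | 0.081 | 1.2 | 2.5 |
| 25 | 0.141 | 0.7 | 1.4 |

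At a coefficient of variation of 100% every z halves. For a change score the SE is multiplied by √(2(1 − ρ)), where ρ is the correlation with baseline. As ρ goes from 0 to 0.7, the 10% case at 300 per arm gives z from 1.7 to 3.2.

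**Who contributes an off-drug OGTT?** Assume that year-6 HbA1c is normal with SD 0.95 and that the arms differ by the plan's 0.5. The proportion stopped is Φ((7.5 − mean)/0.95). The arm means are assumptions.

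| Means, Group I / II | Stopped, I / II | HbA1c difference among those stopped |
|---|---|---|
| 6.0 / 6.5 | 94% / 85% | 0.36 |
| 6.5 / 7.0 | 85% / 70% | 0.28 |
| 7.0 / 7.5 | 70% / 50% | 0.21 |

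If beta-cell function correlates −0.3 to −0.7 with HbA1c, selection alone moves the comparison by about 0.04 to 0.21 SD towards the conventional arm.

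**Would a worst-rank analysis repair this?** Suppose off-drug function is identical in both arms and everyone not stopped shares the worst rank. Let p₁ and p₂ be the proportions stopped and t = n(2 − p₁ − p₂) the number tied. Then

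z = ½n²(p₁ − p₂) / √Var, with Var = (n²/12) × [(2n + 1) − (t³ − t)/(2n(2n − 1))].

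For n = 300 and 85% / 70%: t = 135, Var = 7500 × (601 − 6.8) = 4.46 million, and z = 6750/2111 = 3.2. The three rows of the last table give z of about 1.9, 3.2 and 4.4 at 300 per arm, and 1.0, 1.6 and 2.2 at 76. On-drug HbA1c at year 6 would drive the result, so this analysis has the same fault as the year-3 comparison.

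**The case against.** - **On-treatment change is a legitimate target.** The trial compares two continuing strategies, section 1 speaks of improvement, and the Abstract's wording is met by improvement or preservation. This stands, and it is why endpoint 3 should be labelled rather than dropped. A reader might infer that the plan commits itself to declaring preservation from the year-3 test. It does not: the Data Analysis section plans no such statement, and the Abstract only predicts one.
- **The direction of bias is not known.** A reader might infer that the comparison must favour Group I. The documents do not support that. Group II may be on glipizide or insulin, so the acute contrast could be small, absent or reversed. This stands.
- **Test-day doses may not have been taken.** The OGTT is at 08:00 after an overnight fast, and exenatide and glipizide are tied to meals. The documents do not say whether the morning dose is held, so the acute effect could be smaller than illustrated. The Group I risk table in section 6c also lists a once-weekly exenatide form, for which a missed morning dose would not mean off drug. The point is unresolved.
- **A constant acute effect would cancel from the year-3 to year-6 change.** This is correct in principle, but titration and added insulin between those visits limit it.
- **The magnitude rests on assumed effects.** This stands; the calculation shows only what would be detectable.

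**Conclusion.** The concern holds in a limited form. As scheduled, endpoint 3 measures beta-cell response under continuing therapy that differs by arm. Alone it can support improvement on treatment but not preservation. The illustrative size is z of about 4.9 (300 per arm) or 2.5 (76 per arm) for a purely acute 20% effect, and 2.4 or 1.2 for 10%. This assumes a coefficient of variation of 50%, no durable effect, and no offsetting drug action in Group II.

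That testing is on treatment is inferred from the schedule and the absence of any stated drug hold. That the off-drug OGTT is unused is inferred from the silence of the endpoint list and the analysis section. It would go too far to read the washout OGTT as a clean randomised answer, because its off-drug subset is selected by year-6 HbA1c. The matter is secondary, and the primary HbA1c comparison is unaffected.

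**What to change.** 1. Define endpoint 3 at years 3 and 6 as on-treatment beta-cell response. Record the drug state on the test day. Rely on the C-peptide-based index (ΔISR/ΔG), because injected insulin distorts the plasma-insulin indices. It also distorts the Matsuda factor, and so the ISR-based disposition index. ΔISR/ΔG does not remove acute secretagogue action, so draw no preservation conclusion from it alone.
2. Pre-specify the planned OGTT 3 months after stopping as the supportive off-drug evidence, reported by arm and adjusted for baseline. Show the numbers and characteristics of those not stopped and of those lost earlier. Give sensitivity bounds over a stated range of off-drug values for these participants, and state that the subset is selected after randomisation. Do not use a worst-rank analysis as the test of preservation.
3. Reconcile three points: the two OGTT frequencies in the Washout Phase (six-monthly and two-yearly); HbA1c of exactly 7.5%, which no rule covers; and follow-up of treatment failures, who continue all visits under section 6a but, under section 7, return to their own doctor if A1c stays above 8% on full-dose therapy.

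The cost is SAP wording and one supportive analysis, with no new test and no change to treatment. The downside is that the preservation answer comes later, from fewer and selected participants, and is only supportive.

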If, at any time after achieving a HbA_{1C} $\leq 6.0\%$, the HbA_{1C} rises above 6.0% and the subject is on submaximal doses of metformin or pioglitazone or exenatide, the medication(s) will be titrated up to the maximally effective dose and the subject will not be considered a treatment failure.

If, after month six, the HbA_{1C} $\geq 6.0\%$ and the subject is on maximum doses of all triple therapy medications, the subject will be considered a treatment failure. If, after month 6, the HbA_{1C} rises to $> 6.5\%$, bedtime glargine insulin (10-20 units) will be started and titrated to a maximum of 60 units to achieve a FPG < 110 mg/dl and HbA_{1C} $< 6.0\%$. If more than 60 units of glargine insulin is required to reduce the HbA_{1C} $< 6.5\%$, regular insulin will be added to each meal and adjusted based upon the pre- and post-meal blood glucose levels. These "treatment failure" subjects will continue with all follow up visits/procedures. Throughout the titration process, downward adjustments will be allowed for the development of hypoglycemia, as defined by a blood glucose less than 60 mg/dl with (symptomatic hypoglycemia) or without (asymptomatic hypoglycemia) symptoms. Serious hypoglycemia is defined as any hypoglycemic reaction requiring assistance from a third party for recovery.

GROUP II: Group II will be started on metformin, 1000 mg with breakfast and 1000 mg with supper.

If, after month one, the FPG ≥ 110 mg/dl or HbA_{1C} $\geq 6.0\%$, glipizide (5 mg) will be added: 1-2 tablets with breakfast depending on the FPG, HbA_{1C}, and discretion of the investigator in order to avoid hypoglycemia.

If, after month two, the FPG ≥ 110 mg/dl or HbA_{1C} $\geq 6.0\%$, the glipizide dose will be increased to 4 tablets (20 mg/dl).

If, after month three, the FPG > 110 mg/dl or HbA_{1C} $> 6.0\%$, bedtime basal insulin (10-20 units) will be started and titrated up to achieve a FPG < 110 mg/dl or HbA_{1C} $< 6.0\%$

If, at any time after achieving a HbA_{1C} $< 6.0\%$, the HbA_{1C} rises above 6.0% and the subject is on submaximal doses of metformin or glipizide or glargine insulin, the medication(s) can be titrated up to the maximally effective dose and the subject will not be considered a treatment failure.

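### Treatment failure is defined three incompatible ways, secondary endpoint 2 is not arm-neutral, and the Cox event has no HbA1c threshold

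*Combined protocol and SAP*

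**What the plan says.** Three passages define treatment failure.

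- **Section 6a, treatment algorithms.** In Group I, after month six with HbA1c at or above 6.0%, if "the subject is on maximum doses of all triple therapy medications, the subject will be considered a treatment failure". In Group II, after month six with HbA1c above 6.0%, if "the subject is on maximum doses of metformin, glipizide, and glargine insulin, the subject will be considered a treatment failure". In both arms these subjects stay in all follow-up.
- **Section 6a, Secondary End Points, item 2.** "Number of treatment failures in each group as defined by HbA_{1c} >6.0% and requiring the addition of rapid acting insulin with meals".
- **Section 7(1), item 7.** A1c remaining above 8% on full-dose therapy in either arm. The subject goes back to their own doctor for standard care.

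Both algorithms exempt subjects on submaximal doses. The Group I maxima are printed in Section 3: "up-titrated to 45 pioglitazone plus 2000 metformin and 10 mcg s.c. bid exenatide to achieve HbA1c" below 6.0%. The Group II exemption covers metformin, glipizide "or glargine insulin, the medication(s) can be titrated up to the maximally effective dose and the subject will not be considered a treatment failure". Group II "bedtime basal insulin (10-20 units) will be started and titrated up to achieve" its targets, with no maximum given. The only basal-insulin ceiling is in the Group I text, for insulin added to triple therapy once HbA1c exceeds 6.5%: "bedtime glargine insulin (10-20 units) will be started and titrated to a maximum of 60 units to achieve" its targets.

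Mealtime insulin is reached differently in the two arms. In Group I it follows only if more than 60 units of glargine would be needed to get below 6.5%. In Group II, "Regular insulin will be added to each meal when the HbA_{1C} rises to" above 6.5%.

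Data Analysis and Statistical Methods fits a Cox model to failure to maintain the treatment goal and prints no value. The goal is below 6.5% in Section 1 (objective 1) and Section 2, and below 6.0% in Section 3 and the Abstract.

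**The concern.** Durability is in the study title, and a lower rate of therapeutic failure is a stated hypothesis in the Abstract. Secondary endpoint 2 and the Cox model are where the plan would test these. If the event can be read several ways, two analysts following the plan can produce different counts. If the event also depends on which drugs an arm is allowed before mealtime insulin, the count partly measures the algorithm and not only glycaemic control.

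A further difficulty is that the Abstract's secondary outcome is failure to achieve the goal, whereas the Cox model concerns failure to maintain it. These are different events: a subject who never reaches goal has the first, and may or may not have the second.

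**Working it through.** **The plan's own figure.** The only sample size is 76 completers per arm, for the primary HbA1c difference. Inputs: difference 0.5, SD 0.95 (the printed 60.95 read as plus or minus 0.95), two-sided alpha 0.05, and power assumed to be 90% because none is stated. n = 2 × (1.960 + 1.282)² × 0.95² / 0.5² = 75.9, so 76. It reproduces. It does not involve treatment failure, and no calculation is given for the failure endpoint.

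**Two cases that need no distribution.** Take month 9, with no mealtime insulin yet.

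| Rule | HbA1c 6.3% | HbA1c 7.0% |
|---|---|---|
| Section 6a label, arm's drugs at maximum | failure in both arms | failure in both arms |
| Section 6a label, any assigned drug submaximal | not a failure in either arm | not a failure in either arm |
| Secondary endpoint 2, assigned drugs at maximum | neither arm (mealtime insulin not triggered) | Group II yes; Group I no (glargine comes first) |
| Section 7 | neither arm | neither arm |
| Goal below 6.5% | met | missed |
| Goal below 6.0% | missed | missed |

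The 6.3% column shows that the definitions disagree, and that the 6.0% in endpoint 2 triggers mealtime insulin in neither arm. The 7.0% column shows that endpoint 2 classifies the same value on each arm's full assigned regimen differently.

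**Size, by illustration.** Assume on-treatment HbA1c is normal with mean 6.3 and SD 0.95; the documents give no on-treatment distribution. Then P(≥6.0) = 0.624, P(>6.5) = 0.417, P(>7.0) = 0.231, P(>7.5) = 0.103.

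1. *Threshold.* Share between the two goals: 0.624 − 0.417 = 0.207. Over means 6.0 to 6.6 and SDs 0.8 to 1.1 the range is 17% to 24% of an arm.
2. *Endpoint 2, equal HbA1c on the assigned regimens, all at maximum doses.* Group II is counted if X > 6.5: 41.7%. Group I is counted only if glargine, lowering HbA1c by an assumed d, still leaves it above 6.5, that is X > 6.5 + d: 23.1% at d = 0.5 and 10.3% at d = 1.0. The gaps are 18.6 and 31.3 points (14 to 42 points over the same grid). If instead the arms are equal on their non-insulin drugs and glargine works equally well in both, each arm passes through glargine first and the gap is nil.
3. *Section 6a label, equal HbA1c.* With exempt shares q1 and q2 in Groups I and II, the counted rates are 0.624 × (1 − q1) and 0.624 × (1 − q2), so the gap (Group I minus Group II) is 0.624 × (q2 − q1). At 25% in both arms: 46.8% against 46.8%, no gap. At 25% in Group I and 10% in Group II: 46.8% against 56.2%, so Group I is 9.4 points lower. Swapping the shares reverses the sign. The documents give neither share.

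**The case against.** The best reply is that only item 2 is attached to an endpoint. On that view the algorithm label guides titration, Section 7 is a safety rule, and the Cox wording points to the Abstract's stated goal of 6.0%. This has some force: no passage says the algorithm label is what will be analysed. It does not rescue item 2, whose insulin condition can be applied only through the algorithms, and those differ by arm. The Abstract is a plausible source for the Cox threshold, but objective 1 is the passage that speaks of maintaining control, and it says 6.5%.

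A reader might infer that the algorithm label is built against Group I, because Group II's exemption includes glargine with no printed maximum. The documents do not support that. Group I has the same kind of exemption, and it can be lasting: Section 6a allows a reduced exenatide dose, titrated to what is tolerated, for subjects with gastrointestinal side effects, and the risk table lists nausea as likely. Nor is it a definitional bias that Group I can fail before insulin while Group II must first be on glargine. Basal insulin is part of the strategy that Section 2 assigns to Group II, so a lower HbA1c from it is a real difference between strategies.

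A reader might also infer that the Section 7 rule removes subjects from follow-up and distorts the primary comparison. The text says they return to their doctor; it does not say that study visits stop. The conflict with Section 6a has to be reconciled, but a shift in the primary result is not established.

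**Conclusion.** The concern holds for secondary endpoint 2 and the Cox model. The three definitions cannot all be applied, item 2 gives different answers in the two arms at the same HbA1c above 6.5% on the full assigned regimens, and the Cox threshold is unstated with two competing values. These conclusions rest on the text alone.

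The sizes are illustrations that rest on the assumed distribution and glargine effect. The submaximal-dose exemption makes the algorithm label dependent on dose status, but the direction and size of any tilt are unknown. The primary endpoint definition and the 76 per arm are unaffected. The point should be fixed, but it does not threaten the primary analysis.

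**What to change.** For secondary endpoint 2 and the Cox model, use one HbA1c-only event, the same in both arms: the first scheduled 3-monthly visit after month six with HbA1c not below 6.5%, the goal in objective 1. Show the same analysis at 6.0%, the Abstract's goal, beside it. Report subjects above goal at month six separately as not having attained it. Count any subject who leaves under the Section 7 criterion, at any time, as an event.

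Add a version confirmed at the next visit as a sensitivity analysis only. Therapy is adjusted on each visit's HbA1c, so confirmation can erase genuine crossings: if the step taken lowers HbA1c by 0.5 or 1.0, the illustration loses 1 − 0.231/0.417 = 45% or 1 − 0.103/0.417 = 75% of them.

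Report mealtime-insulin starts and maximum-dose status by arm descriptively. Give the Section 7 criterion another name, and reconcile Sections 6a and 7 on whether failures stay in follow-up. No treatment step is changed.

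The cost is rewording item 2, the Cox paragraph and one line of Section 7; no new data are needed. Unconfirmed crossings are noisier. Over the 10 quarterly visits from month 9 to month 36, with independent errors and an assumed within-subject SD w of 0.1 to 0.2, the chance of at least one false crossing is 1 − (1 − p)^10, where p = P(Z ≥ (6.5 − μ)/w). That is 0% to 6% for a subject stable at μ = 6.0 and 1% to 50% at μ = 6.2. At equal true HbA1c and equal measurement error this noise is the same in both arms. Counts will differ from those under the current wording. The statistical section is in the past tense, so if the data have already been analysed, label the new analysis post hoc and show it beside the original.
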